#### ***Analysis of all treatment emergent serious adverse event(s)***

- All treatment-emergent serious adverse events by primary SOC and PT, showing the number (%) of patients with at least 1 treatment-emergent serious adverse event, sorted by the internationally agreed SOC order and by decreasing incidence of PTs within each SOC
- All treatment-emergent serious adverse events regardless of relationship and related to IMP, by primary SOC and PT, showing the number (%) of patients with at least 1 treatment-emergent serious adverse event, sorted by the internationally agreed SOC order.
- By-patient listing of all serious treatment-emergent adverse events

#### ***Analysis of all treatment-emergent adverse event(s) leading to permanent treatment discontinuation***

- All treatment-emergent adverse events leading to permanent treatment discontinuation, by primary SOC, HLGT, HLT, and PT, showing the number (%) of patients sorted by the internationally agreed SOC order. The other levels (HLGT, HLT, PT) will be presented in alphabetical order
- By-patient listing of all treatment-emergent adverse events leading to permanent treatment discontinuation

#### ***Analysis of treatment-emergent adverse events of special interest***

- All pre-specified treatment-emergent adverse events of special interest, by primary SOC and PT, showing the number (%) of patients, sorted by the internationally agreed SOC order and by decreasing incidence of PTs within each SOC
- By-patient listing of all treatment-emergent adverse events of special interest

#### ***Analysis of all post-treatment adverse events***

- Overview of post-treatment adverse events, summarizing number (%) of patients with any
  - Adverse event
  - Serious adverse event
  - Adverse event of special interest (AESI)
  - Adverse event leading to death
  - Severe adverse event
- By-patient listing of all post-treatment adverse events

#### **2.4.5.2 Deaths**

The following summaries of deaths will be generated for the safety population.

- All adverse events leading to death (death as an outcome on the adverse event case report form page as reported by the Investigator) by primary SOC and PT showing the number (%) of patients sorted by the internationally agreed SOC order and by decreasing incidence of PTs within each SOC
- Treatment-emergent adverse events leading to death (death as an outcome on the adverse event case report form page as reported by the Investigator) by primary SOC and PT showing the number (%) of patients sorted by the internationally agreed SOC order and by decreasing incidence of PTs within each SOC
- Number (%) of patients who died by study period (on-study, on-treatment)
- By-patient listing of all AE leading to death

#### **2.4.5.3 Analyses of laboratory variables**

The summary statistics (including number, mean, median, standard deviation, minimum and maximum) of all laboratory variables (central and local laboratory values and changes from baseline, percentage change from baseline) will be calculated for each visit or study assessment (baseline, each postbaseline time point) in overall group. Both study baseline and eliglustat baseline will be applied to the summary statistics.

By-patient listings for those patients with abnormal laboratory values will be provided by category of laboratory tests. Hemoglobin and platelet test result will be analyzed as above separately. A by-patient data listing of all pregnancy testing for female patients will be produced.

#### **2.4.5.4 Analyses of vital sign variables**

No vital sign variables are collected in this study.

#### **2.4.5.5 Analyses of electrocardiogram variables**

No electrocardiogram variables are collected in this study.

#### **2.4.5.6 Analyses of other safety endpoints**

##### **2.4.5.6.1 Physical examinations**

A summary statistics of physical exam findings interpretations will be presented by visit for each body system.

#### **2.4.5.6.2 Weight, height and BMI**

A summary statistics of absolute value, changes from baseline and percentage change from baseline (study baseline as well as Eliglustat baseline) in height, weight and BMI will be analyzed by visit.

#### **2.4.5.6.3 Complete neurological examination**

A summary statistics of quantitative neurological examinations findings will be presented by visit.

### **2.4.6 Analyses of pharmacokinetic and pharmacodynamic variables**

No scheduled PK data are collected in this study. But unscheduled PK samples may be collected in individual cases after discussion between the investigator and Genzyme. By-patient listing may be provided if necessary.

### **2.4.7 Analyses of quality of life/health economics variables**

The score for each scale will be estimated from the Short Form-36 Health survey [SF-36]. The overall physical component scale (PCS) and mental component scale (MCS) will be computed. Summary statistics as well as change and percentage change from baseline (study and eliglustat) by visit by all SF-36 QOL variables will be presented.

## **2.5 DATA HANDLING CONVENTIONS**

### **2.5.1 General conventions**

The following formulas will be used for computation of parameters.

For all safety and efficacy parameters, values that are reported as BQL (below quantification level) or LLOQ (lower limit of quantification) will have numeric values set equal to the BQL or LLOQ lower limit (eg, if BQL < 2, then value will be set equal to 2). However, the original value will be displayed in by-patient data listings.

The only exception is for chitotriosidase values. Patients who have a chitotriosidase genotyping category of “Homozygous Mutation” have no expected chitotriosidase activity. Therefore, patients who have a value of BQL reported will have numeric values set equal to missing.

#### ***Demographic formulas***

Age will be presented as the number of years between date of birth and the reference date. The following ages (in years) may be computed using the formula [(Study (EXOSKEL) reference date – date of birth) + 1 day]/365.25, with reference dates indicated as follows:

Age	Reference Date
Age at study informed consent	Date of study informed consent
Age at Day 1 study dose	Date of first Eliglustat dose of the study
Age at Gaucher disease diagnosis	Date of Gaucher Disease Diagnosis
Age at first Gaucher disease symptom onset	Date of First Gaucher Disease Symptom Onset

If the date of diagnosis is not complete or date of symptom onset is not complete then age at diagnosis or symptom onset will be determined by the month and/or year of date of birth and diagnosis or symptom onset.

Certain assessments may be summarized by age categories which will be determined prior to database lock based on the frequency of ages reported (eg,  $\leq$  median age for all patients,  $>$  median age for all patients).

### ***Vital signs formulas***

Weight in pounds will be multiplied by 0.4536 to be converted to kilograms (kg); and height in inches will be multiplied by 2.54 to be converted to centimeters (cm).

BMI (kg/ m^2) will be calculated using the following formula:

$$\text{BMI} = \frac{\text{Weight (kg)}}{\text{Height (m}^2\text{)}}, \text{where } \text{height (m}^2\text{)} = (\text{height (cm)} \times 0.01)^2$$

#### **2.5.2 Data handling conventions for secondary efficacy variables**

##### ***Eliglustat baseline for hemoglobin and platelet count for patients originated from Phase 2 and Encore study***

To obtain a single Study Baseline value for Hemoglobin and Platelet Count, the average of the last two measurements prior to receiving Day 1 dose of Eliglustat in the study will be calculated. This average value will be referred to as the Baseline value. If either of the 2 measurements is missing, the Study Baseline value will refer to the non-missing value.

To obtain a single Eliglustat Baseline value for Hemoglobin and Platelet Count, the average of the last two measurements prior to receiving Day 1 dose of Eliglustat in the previous Phase 2 or Phase 3 trials will be calculated. This average value will be referred to as the Eliglustat Baseline value. If either of the 2 measurements is missing, the Eliglustat Baseline value will refer to the non-missing value.

##### ***Formulas for calculation of organ Multiples of Normal (MN)***

The following equations will be used to calculate multiples of normal (MN) values for spleen and liver volume. If a patient does not have weight assessed on the same date as the spleen/liver volume assessment, the weight having the closest date to the spleen/liver assessment will be used.

$$\text{Spleen Multiple of normal} = \frac{\text{Volume [cc]}}{2 \times \text{weight [kg]}}$$

$$\text{Liver Multiple of normal} = \frac{\text{Volume [cc]}}{25 \times \text{weight [kg]}}$$

### 2.5.3 Missing data

For categorical variables, patients with missing data are not included in calculations of percentages unless otherwise specified. When relevant, the number of patients with missing data is presented.

***Handling of computation of treatment duration if investigational medicinal product end of treatment date is missing*** For the calculation of the treatment duration, the date of the last dose of IMP is equal to the date of last administration reported on the end-of-treatment case report form page. If this date is missing, the exposure duration should be left as missing.

The last dose intake should be clearly identified in the case report form and should not be approximated by the last returned package date.

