- The patient experiences a decline in Gaucher disease status that, in the opinion of the Investigator, warrants discontinuation from the study (eg, repeated bone crises, clinically significant increases in liver or spleen volumes).

Patient who discontinue or withdraw from participation in the study will be contacted in order to obtain information about the reason(s) for discontinuation/withdrawal and for collection of AEs, if any. The patient will be asked to return to the clinic to complete all study discontinuation/withdrawal assessments. The Investigator will describe the reason for

discontinuation on the Completion/Discontinuation case report form. Patients who discontinue/withdraw participation from the study will not be replaced. A summary of all discontinuations will be included in the final study report.

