10.4.3 Criteria for permanent treatment discontinuation

The patients may withdraw from treatment with the IMP if they decide to do so, at any time and irrespective of the reason, or this may be the Investigator's decision. All efforts should be made to document the reasons for treatment discontinuation and this should be documented in the e-CRF.

The use of eliglustat is prohibited in combination with Class IA and Class III antiarrhythmic medications. See [Section 8.5.1.1](#) for detail.

Patients requiring medications incompatible with eliglustat because of drug-drug interaction for longer than 2 weeks should be discontinued from the study. See [Section 8.5.1.2](#) for detail.
Handling of patients after permanent treatment discontinuation

Patients will be followed-up according to the study procedures as specified in this protocol up to the scheduled date of study completion, or up to recovery or stabilization of any AE to be followed-up, whichever comes last, unless the patient is lost to follow up.

If possible, and after the permanent discontinuation of treatment, the patients will be assessed using the procedure normally planned for the last visit at study completion or patient discontinuation/withdrawal.

All cases of permanent treatment discontinuation should be recorded by the Investigator in the appropriate pages of the CRF when considered as confirmed.

10.4.4 Procedure and consequence for patient withdrawal from study.

The patients may withdraw from the study before study completion if they decide to do so, at any time and irrespective of the reason.

If possible, the patients are assessed using the procedure normally planned for the visit at study completion or patient discontinuation/withdrawal.

For patients who fail to return to the site, the Investigator should make the best effort to recontact the patient, and to determine his/her health status, including at least his/her vital status. Attempts to contact such patients must be documented in the patient's records (eg, times and dates of attempted telephone contact, receipt for sending a registered letter).

The statistical analysis plan will specify how these patients lost to follow-up for their primary endpoints will be considered.

Patients who have withdrawn from the study cannot be enrolled again in the study. Their inclusion and treatment numbers must not be reused.

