11.4 STATISTICAL METHODS

All endpoints will be summarized descriptively; no hypothesis testing will be performed. Descriptive statistics include those for continuous (n, mean, median, minimum, maximum), categorical (n, percent), cumulative incidence (n, percent) or incidence rate (n/year) outcomes, as appropriate. Calculations and summaries will include all non-missing data at a given time point, imputation will not be performed.

Analysis will be performed on safety and efficacy endpoints at 2 points in this study:

- After the last patient enrolled has completed 2 years of treatment (two-year analysis period)
- When the study is complete

For the PAP, response will be calculated both in reference to study entry (study period) and to first eliglustat treatment (eliglustat treatment period). Because patients will enter this study having been treated with eliglustat for various durations, two baselines will be used:

- Study baseline, defined as status at study entry; and
- Eliglustat baseline, defined as status at first dose of eliglustat in the previous Phase 2 or Phase 3 study.

In reference to the study period, skeletal response will be evaluated for all patients at the 2 year point by measured values (eg, category of bone pain, or bone density value in g/cm²) and changes from baseline (eg, shift in category of bone pain or absolute and percent change from baseline in BMD g/cm² or incidence over 2 years, as appropriate).

In reference to the period of eliglustat treatment, skeletal response will be evaluated 2 years after study entry, but results will be grouped by duration of eliglustat treatment at the time of analysis. The actual groupings will depend on the distribution of treatment duration at the time of analysis, eg, 6 yr., 7 yr., 8 yr. or 6-8 yr., 8-10 yr.

When the study has completed, summaries will be performed for both the total on-study period, and the eliglustat treatment period, as described above.

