### 1.3 DETERMINATION OF SAMPLE SIZE

This study will enroll all eligible patients having completed one of the Phase 2 or Phase 3 trials (approximately 32 patients).

This is a long term extension study. No sample size calculation has been performed. The patients who will be enrolled have already been receiving the IMP for approximately 4 to 8 years prior to the start of the study. The aim of the study is to continue collecting long term data on the efficacy and safety of the IMP.

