#### **2.4.4 Analyses of efficacy endpoints**

In reference to the study period, efficacy result will be evaluated for all patients at the 2 year point by measured values (eg, category of bone pain, or bone density value in g/cm^2) and changes from baseline (eg, shift in category of bone pain or absolute and percent change from baseline in BMD g/cm^2 or incidence over 2 years, as appropriate).

In reference to the period of eliglustat treatment, efficacy result will be evaluated 2 years after study entry, but results will be grouped by duration of eliglustat treatment at the time of analysis. The actual groupings will depend on the distribution of treatment duration at the time of analysis (eg,  $\leq 5$  years versus  $>5$  years).

When the study has completed, summaries will be performed comparing to the 2 baselines as described above if applicable.

All efficacy endpoints will be summarized descriptively; no hypothesis testing will be performed. In general, descriptive statistics (number, mean, standard deviation, minimum and maximum) of the absolute value, change from baseline and/or percentage change from baseline for continuous endpoints will be analyzed. Summary statistics (count, percentage) will be summarized for the categorical endpoints. Cumulative incidence (n, percentage), incidence rate (n/year), or other descriptive statistics will also be displayed as appropriate. Calculations and summaries will include all non-missing data at a given time point, imputation will not be performed.

By-patient data listings containing efficacy endpoints will be produced if necessary.

All the below mentioned other efficacy endpoint analyses will be produced for the full analysis population. Refer to [Section 2.5.3](#) for details on handling dropouts, missing data, and patients who have more than one value assessed within the same time frame.

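### By-visit skeletal shift tables drop patients with no value, and the SAP lacks the promised dropout rule, so worsening that leads to exit can go uncounted

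*SAP*

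**What the plan says.** **Analysis rule.** SAP 2.4.4: "Calculations and summaries will include all non-missing data at a given time point, imputation will not be performed". For categorical variables SAP 2.5.3 says: "For categorical variables, patients with missing data are not included in calculations of percentages unless otherwise specified". It continues: "When relevant, the number of patients with missing data is presented". SAP 2.4.4.1.1 to 2.4.4.1.3 plan shift tables by visit for mobility, bone pain, marrow infiltration category and BMD category.

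**Exit rule.** Protocol 7.3 lists several findings that prompt a joint review by investigator and sponsor of whether a patient should leave the study. One is: "The patient experiences a decline in Gaucher disease status that, in the opinion of the Investigator, warrants discontinuation from the study". The examples given are repeated bone crises and clinically significant enlargement of liver or spleen. Patients who leave are not replaced.

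**Promise.** Protocol 10.4.4, after describing efforts to reach patients who do not return, says: "The statistical analysis plan will specify how these patients lost to follow-up for their primary endpoints will be considered". SAP 2.4.4 sends the reader to SAP 2.5.3 for dropouts. That section covers the percentage rule, treatment duration, medication dates and adverse-event items. SAP 2.2 defines lost to follow-up but not its handling in the efficacy tables. SAP Appendix B lists no supportive analysis for the primary endpoints except an annual incidence rate for lesions.

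**Windows.** SAP 2.5.4, Table 2, Schedule B governs the Gaucher clinical assessments, DXA and MRI. It allows one value per parameter per window, the one nearest the target day. Under Protocol 10.2.5 the withdrawal visit repeats the Gaucher clinical assessments, but bone MRI and DXA only if the last was at least 1 year before.

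**The concern.** There is no control arm, and Protocol 11.4 states: "All endpoints will be summarized descriptively; no hypothesis testing will be performed". The reported distributions and shifts are therefore the result of the study, with no comparison to absorb a selection effect. If a patient leaves because the skeleton got worse, the missing value is a consequence of the outcome being tabulated. Removing that patient from numerator and denominator makes the patients still assessed look better than the cohort that enrolled. The document that was to say how such patients are treated does not do so, and the windowing rule can discard the one assessment made at exit.

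**Working it through.** The plan has no figure to reproduce: the number of patients is a count of those eligible, and SAP 1.3 says "No sample size calculation has been performed". The check has two parts.

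**1. Where an exit value goes under Schedule B**

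Windows rebuilt as midpoints between yearly targets:
- Week 52: target Day 364, window Day 2 to 364 + 182 − 1 = 545.
- Week 104: target Day 728, window 728 − 182 = 546 to 728 + 182 − 1 = 909.

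Both match Table 2. An on-time Week 52 visit (±14 days) lies at most 14 days from Day 364. The consequences by time of exit are:

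| Withdrawal visit | Mobility, pain | Marrow score, BMD |
|---|---|---|
| Before the Week 52 visit | Counts as Week 52; no Week 104 value | Counts as Week 52 if imaged; no Week 104 value |
| About Days 379–545, Week 52 visit done on time | At least 15 days from Day 364, so the Week 52 value is kept and the exit value is not used; no Week 104 value | Not required (under 1 year since imaging); no Week 104 value |
| Day 546 to about Day 728 | Counts as Week 104 | Not required if imaged at about Day 364, so can be missing |

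In the middle row, worsening recorded at exit enters no by-visit shift table.

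**2. How far the denominator rule can move a percentage**

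Let N = 32 (SAP 1.3), m = patients missing at Week 104 and w = worsened among those observed. The documents give neither a dropout rate nor a worsening rate, so m and w are assumptions.
- Reported under the plan: w/(N − m)
- Lower bound, no missing patient worsened: w/N
- Upper bound, every missing patient worsened: (w + m)/N

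| w | m | Reported | Lower | Upper | Upper − reported |
|---|---|---|---|---|---|
| 3 | 1 | 3/31 = 9.7% | 3/32 = 9.4% | 4/32 = 12.5% | 2.8 points |
| 3 | 3 | 3/29 = 10.3% | 3/32 = 9.4% | 6/32 = 18.8% | 8.4 points |
| 3 | 6 | 3/26 = 11.5% | 3/32 = 9.4% | 9/32 = 28.1% | 16.6 points |
| 1 | 6 | 1/26 = 3.8% | 1/32 = 3.1% | 7/32 = 21.9% | 18.0 points |
| 5 | 6 | 5/26 = 19.2% | 5/32 = 15.6% | 11/32 = 34.4% | 15.1 points |

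The gap is about 3 points per missing patient who had worsened (one patient is 1/32 = 3.1%). The lower bound is always slightly below the reported figure: if no missing patient worsened, the plan overstates worsening a little.

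**The case against.** The plan is not silent: using all non-missing data without imputation is a rule, and arguably an answer to Protocol 10.4.4, whose sentence concerns patients lost to follow-up rather than those withdrawn for decline. Stopping treatment does not end observation (Protocol 10.4.3 and 10.5.2), withdrawal for decline is a reviewed decision, the exit visit repeats mobility and pain, and missing counts may be shown. SAP 2.2 also plans listings of discontinuation reasons.

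This narrows the point without removing it. The Protocol 7.3 criterion concerns leaving the study, not only treatment. The exit visit reaches the shift tables only at some timings. Missing counts are shown only when judged relevant, and the listings are not tied to the skeletal tables. A general available-case rule does not supply the dropout details that SAP 2.4.4 says are in 2.5.3.

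A reader might infer three stronger things that the documents do not support:
- **That every percentage is affected.** Adverse-event percentages use the whole safety population (SAP 2.4.5.1) and disposition uses screened patients (SAP 2.2). New or worsening lesions are totalled since study entry with a person-year rate (SAP 2.4.4.1.4), which keeps events detected before exit.
- **That the bias always favours the drug.** It does so when patients leave because of skeletal decline. Exits unrelated to outcome can push the figure slightly the other way.
- **That every withdrawal for Gaucher decline is a skeletal worsening.** Protocol 7.3 also names liver and spleen enlargement. Bone crises are summarised as counts, so even they do not by themselves establish a shift in mobility, pain, infiltration or BMD.

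**Conclusion.** The concern holds for the by-visit shift tables of mobility, bone pain, marrow infiltration and BMD category. They contain only patients with a value at the visit, one exit route can be caused by skeletal disease, the dropout handling to which both documents refer is missing, and the window rule can drop the exit assessment. The tables may understate worsening if patients leave because of skeletal decline.

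Neither the size nor the occurrence of this bias is established. About 3 points per omitted worsened patient follows from N of about 32. The 10.3% with bounds of 9.4% to 18.8% rests on an assumed 3 observed worsened and 3 missing. The exclusion of exit values on about Days 379 to 545 assumes an on-time Week 52 visit. No sample size, alpha or power is involved. This is an inexpensive improvement to a descriptive plan and does not invalidate the design.

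**What to change.** In SAP 2.5.3 and 2.4.4.1:

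1. Use as the shift-table denominator all FAS patients who have the baseline that the table uses, and add rows for patients not assessed, by reason: withdrawn for Gaucher decline; other reason.
2. Add a last-on-study shift summary that includes the withdrawal-visit value even where Table 2 windowing would discard it.
3. Give the Week 104 percentage worsened among observed patients, then as a sensitivity figure that counts as worsened only those withdrawn for skeletal decline in the domain concerned, not those withdrawn for liver or spleen enlargement. Add best-case and worst-case bounds for all missing patients.
4. For means, show at each visit the baseline mean of the patients who contribute.

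No visit, procedure or withdrawal rule changes. Protocol 7.3 already has the reason for discontinuation recorded on the case report form; assigning it to a skeletal domain needs a short review of each case. The cost is SAP wording, some extra table work and possibly slightly less favourable percentages. The last-on-study summary mixes different lengths of follow-up and should be labelled as such.
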